- (ii) Participants have comorbidities (a) developmental impairment (b) learning disability, (c) personality disorders, and/or (d) any clinically significant medical diseases (by case-file review).
- (iii) Participants have organic psychosis or a primary drug or alcohol addiction.

Randomisation and recruitment procedure

Participants referred to the study by ICCMW will be assessed at a screening examination to ensure eligibility and obtain written consent by a research assistant. Eligible participants will undertake a further interview on outcome measures prior to randomization within 3 weeks the commencement of intervention. In order to avoid the contamination of participants, participants allocated to either treatment or control groups will be reminded not to share what they have experienced in the group work among members in the service organization. The subjects will mainly be recruited from three service organizations and thus around 35 from each organization in proportion to the total number of potential participants. Participants will be randomly assigned to receive Mindfulness-based Cognitive Therapy for Psychosis (MBCTp) plus TAU or TAU plus Psychoeducation for Psychosis (PEp). Simple randomization will be used to select subjects from the patient list in each organization to ensure that each participant will have equal opportunity to be included into the study (Altaman and Bland, 1999). A computer-based program (simple randomization) will be used to aid the randomization procedure. Assignment to the study groups will be made independently of staff involved in the recruitment and management of participants in the study. Raters who collect follow-up data will also be blind to the identity of participants. Considerable efforts will be made to ensure the blindness of raters such as storage of data will be kept separate from the therapists and raters who will be working in different rooms. All data will be locked in a cabinet with limited access only by responsible raters and recorded in a logbook.

Sample size

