Sample size has been estimated on the basis of previous clinical trials of mindfulness interventions for people with psychosis, in which the primary outcome of depression and anxiety (effect size=0.76), and distress relating to psychotic symptoms (effect size=0.50) were the main outcomes (White et al., 2011; Chadwick et al., 2016). Study power calculation indicated that 82 participants (n=41 per group) were required to detect statistically significant differences on emotional distress between two groups with effect size of 0.63 at post-intervention, p=0.05 and power of 0.80 (Stevens, 2009). Taking account of a 15% attrition, the total sample size required should be 95 (n=48 per group).

Interventions

MBCTp will be delivered to the study groups while PEp will be delivered to the control groups. Intervention groups will be facilitated by the researcher who is experienced in cognitive therapy and mindfulness. The psychoeducation group will be conducted by a research assistant (RA1) who is an experienced psychiatric nurse and is trained by the researcher and an experienced psychoeducation researcher. All sessions will consist of 12-weekly 1.5- hour sessions, plus 12-week practice at home with guided CDs which comprises short mindfulness practice (Chadwick et al, 2016). Mindfulness practice will be with guided verbal instructions offered every couple of minutes to avoid prolonged silence. Mandatory individual home practice will be devised and completion of homework will also be assessed by counting the number of submissions and percentage of

completion per program. The session content will be protocolled according to the origins of MBSR (Kabat-Zinn, 2013) and MBCT (Teasdale, Williams and Mark, 2014) (Appendix 1). It will also be validated by a panel of experts including psychiatrists, clinical psychologists and psychiatric nurses who are experienced in mindfulness and cognitive therapy. Psychoeducation (psychosis) (PEp) will be developed based on the manuals produced by the Early Psychosis Prevention and Intervention of the Early Psychosis Prevention and Intervention Centre (EPPIC) National Support Program (ENSP), Australia and the psychoeducation manual produced by the Foundation for Life Sciences, University of Technology Sydney, Australia (Creek et al, 2015; Perry et al, 2012). It will be validated by a panel of experts and previewed by 5-10 service users in the pilot study.

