Mediation analyses will be conducted to examine covariates of change in emotions and distress associated with psychotic symptoms by multiple regression analysis. Within – subjects effect sizes will also be reported based on Cohen's d statistic. Kaplan Meier survival analysis will be used for the analysis of re-hospitalization rates across treatment and control groups. The significance level of all statistical tests will be set at 5%. Clinical significance will be all subscales of DASS-21 shows a percentage improvement in mean scores in the range of approximately 45–55% pre- and post-intervention (Ng, Trauer, Dodd, Callaly, Campbell and Berk, 2007). For example, the mean DASS severity ratings of depression in pre-intervention is 31.2 and 16.2 in a week post-intervention. The difference is 15.0 and the percent change is 48.1 which is clinical significant. Reliable Change Index (RCI) will take into account the reliability of assessment instrument on scores of each participant between the pre-test and one post-test divided by the standard error of the difference between the two scores. Any value of RCI >1.96 (at p<0.05) will be considered statistically significant (Jacobson & Truax, 1991).

NVivo will be used to analyze the qualitative data on subjective experiences to mindfulness and acceptability to the interventions (Krippendorff, 2004). All audio-taped interviews will be transcribed into Cantonese/Chinese by the research assistant and checked for accuracy of transcription by the researcher. The revised transcripts

will be coded independently and important manifest and meanings in the data will be identified.

Ethical considerations

Approval for human subject research will be obtained from the three ICCMWs and Edinburgh Napier University before the start of data collection. The researcher will ensure and inform the potential participants that participation in the study is voluntary and that withdrawal from the study at any time will not affect any aspects of care. The information leaflet and consent form will be developed according to the format recommended by School of Health and Social Care ethics committee. All participants will be assured of the confidentiality of the data provided and the anonymity of their personal identity, and asked for permission to tape record the interviews and intervention sessions if selected. All data will be safely kept in a locked cabinet accessible only by the researcher.

Adverse events reporting and monitoring

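### The attrition-adjusted sample size of 95 (48 per group) contradicts itself and falls just short of the 82 evaluable participants it is meant to protect

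*SAP*

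**What the plan says.** The Sample size section of the SAP gives the base requirement as "82 participants (n=41 per group) were required to detect statistically significant differences on emotional distress between two groups", "effect size of 0.63 at post-intervention, p=0.05 and power of 0.80". It then adjusts for loss: "Taking account of a 15% attrition, the total sample size required should be 95 (n=48 per group"). It does not say how the adjustment was made.

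The section on randomisation and recruitment, just before it, says that participants will come mainly from three service organizations, with "around 35 from each organization in proportion to the total number of potential participants". The same section specifies simple randomization.

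**The concern.** A sample size adjusted for attrition has one job: if the stated share of participants is lost, the number required for the analysis should remain. This one does not quite do that, and its total and its per-group figure disagree within one sentence. The trial is two-arm, so no third group explains the gap of one.

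The number matters because recruitment will be judged against it and the report will quote it. A reader checking the figures finds two totals (95 and 96), neither of which gives the 82 the section has just required. The recruitment text adds an approximate per-organization figure that matches neither.

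**Working it through.** **Inputs, all from the Sample size section:** standardised effect 0.63; significance level 0.05; power 0.80; 82 evaluable (41 per group); attrition 15%; adjusted total 95 (48 per group). Sidedness is not stated; two-sided is assumed.

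**1. Base size.** A two-sample t-test with d = 0.63, two-sided 0.05 and power 0.80 needs 40.53 per group, so 41 per group and 82 in total. This reproduces the plan exactly. A one-sided test would need 32 per group, so the two-sided reading is the one that fits.

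**2. How 95 and 48 arise.** Multiplying by 1 + 0.15 and rounding up:

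- 82 × 1.15 = 94.3, so 95
- 41 × 1.15 = 47.15, so 48

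Both printed figures are reproduced. Rounding the total and the group size up separately also explains why 95 is not 2 × 48 = 96. That the multiplier was used is an inference from this match.

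**3. The adjustment that 15% loss requires.** If N are enrolled and 15% are lost, 0.85 × N remain, so N = n / 0.85:

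- total: 82 / 0.85 = 96.47, so 97
- per group: 41 / 0.85 = 48.24, so 49, which is 98 with equal arms

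**4. What each total delivers at 15% loss, with equal arms.**

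| Enrolled | Expected evaluable | Per group | Power, d = 0.63 |
|---|---|---|---|
| 95 | 80.75 | 40.375 | 79.8% |
| 96 | 81.6 | 40.8 | 80.3% |
| 97 | 82.45 | 41.225 | 80.7% |
| 98 | 83.3 | 41.65 | 81.1% |

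For reference, exactly 41 per group gives 80.5%. The expected shortfall against 82 is 82 − 80.75 = 1.25 participants at 95, and 82 − 81.6 = 0.4 at 96.

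**5. Attrition that the printed totals do cover.**

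- 95: 1 − 82/95 = 13.7%
- 96: 1 − 82/96 = 14.6%

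**6. The per-organization figure.** 3 × 35 = 105, and 105 × 0.85 = 89.25, or about 44.6 per group, with power 83.7%. A total of 95 spread over three organizations would be about 32 each (95 / 3 = 31.7).

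**The case against.** The strongest reply is that nothing of substance turns on this. Power of 0.80 needs 40.53 per group before rounding, and 48 per group leaves 40.8, so the nominal power is met at that figure (80.3%). At 95 it is 79.8%, which to two decimals is still the plan's 0.80. That stands, and it limits the point to a correction.

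A reader might infer that the trial fails to reach its stated power. The documents do not support that as a general statement. With equal arms, the miss occurs only at 95 and is about 0.2 percentage points. Simple randomization does not guarantee equal arms. Averaging over 1:1 chance allocation and independent 15% loss gives mean power of 79.3% at 95, 79.7% at 96, 80.1% at 97 and 80.5% at 98. This puts both printed totals slightly under 0.80, but still by less than one point. For the same reason, 49 per group is a planning figure that simple randomization would not ensure.

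A reader might also want to count about 105 as a third, competing target. The recruitment text does not state that total. Its wording (mainly, around, in proportion) describes an approximate plan by organization, not a rule for closing recruitment. Recruiting 105 would more than cover the shortfall. However, the Sample size section does not mention or justify 105, so it does not repair the stated requirement.

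The reply leaves the arithmetic untouched: 95 is not twice 48, and neither 95 nor 96 retains 82 after 15% loss.

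**Conclusion.** The adjusted sample size is wrong as written. The total and per-group figures are inconsistent by one, and both fall short of the section's own requirement at its own attrition rate. The correct total is 97, or 98 with equal groups: 2 or 3 more than the stated 95.

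The consequence is minor. Relative to 41 per group, expected power drops by about 0.6 points at 95 (80.5% to 79.8%) and 0.2 points at 96 (80.5% to 80.3%). The base figure of 82 is correct for its inputs.

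These power figures assume a two-sided t-test at the post-intervention assessment, equal arms and loss at exactly its expected value. The inconsistency between 95 and 48 per group, and the failure to retain 82, rest on none of these assumptions beyond the stated 15%.

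**What to change.** Change one sentence in the Sample size section, in one of two ways:

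- State the target as 82 / 0.85, giving 97 in total, or as 41 / 0.85, giving 49 per group and 98 in total.
- Keep one of 95 or 96, remove the other, and state the attrition under which 82 are retained: 13.7% for 95 or 14.6% for 96.

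In either case, name the formula and the sidedness of the test. In the recruitment section, make the approximate number per organization agree with the chosen total (98 / 3 is about 33), or say that about 105 is a deliberate margin above it.

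The cost is editorial. The recruitment plan already reaches about 105, so a target of 97 or 98 asks for no recruitment beyond what is foreseen, and no analysis changes.

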The WHOQOL-100 (Li, Young, Xiao, Zhou and Zhou, 2004) which is a self-administered questionnaire consisting of 100 items and among them, there are six domains: physical, psychological, level of independence, social relationship and environmental and spirituality. The internal consistency is acceptable ($\alpha=0.76 - 0.90$ across domains) and the validity is strong ($\alpha = 0.72 - 0.82$) across all domains.

Positive and Negative Syndrome Scale (PANSS) (Kay, Fiszbein and Opler, 1987; Kay, Fiszbein and Opler, 2007) is a 30-item, 7-point scale measuring positive and negative syndrome, differentiation of clinical symptoms and severity of illness. The seven rating points represent increasing levels of psychopathology from 1 (absent) to 7 (extreme). The PANSS ratings will be derived from clinical interview, clinical reports or family members over the past one week. The overall alpha coefficients for the Positive and Negative Scales are 0.73 and 0.83 ($p<0.001$) respectively.

Acceptance and Action Scale (AAQII) (Bond et al., 2011). A seven-item questionnaire that is a commonly used self-report measure of experiential avoidance which also measures psychological inflexibility. The items are rated on a 7-point Likert scale from 1 (never true) to 7 (always true). Its internal consistency is $\alpha=0.78 - 0.88$, while test-retest reliability is 0.81 and 0.79 for 3 and 12 months respectively. The internal consistency of a Chinese translated version for college students and athletes is $\rho= 0.88$ and $\rho=0.85$ respectively. The test-retest reliability is $\gamma=0.86$ and $\gamma=0.74$ across an average period of one month for college students and athletes (Zhang et al, 2014).

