Five Facet Mindfulness Questionnaire (FFMQ) (Baer et al, 2006) is a 39-item self-report questionnaire that measures five facets of mindfulness: observing; describing; acting with awareness; non-judging and non-reacting. The internal consistency for each of the five facets are $\alpha=0.83$, $\alpha=0.91$, $\alpha=0.87$, $\alpha=0.87$ and $\alpha=0.75$ accordingly. Items are scored on a 5-point Likert scale ranging from 1 (never or very rarely true) to 5 (very often or always true). The Chinese version of the Five Facet Mindfulness Questionnaire (FFMQ-C) obtained a good test-retest reliability (0.88) and a high internal consistency (0.83 in the community sample and 0.80 in the clinical sample) (Hou, Wong, Lo and Mak, 2013). A short form scale of the FFMQ (FFMQ-SF) is highly and significantly correlated with the FFMQ-C ($r=0.96$), and explained 91.3% of the variance of the FFMQ-C which will be adapted for the purposes of the study.

The last outcome assessment will be the number and length of re-hospitalization referenced from the case files and self-reporting.

Regarding the qualitative data obtained by focus group interviews, it will be used to determine the common themes being mentioned most frequently by participants and organized under different categories such as expectations, positive and negative outcomes, personal difficulties, positive and negative comments about the program and description.

Data collection procedure

There will be two research assistants (RA), RA1 will be responsible for conducting the psychoeducation program and RA2 will be blinded and doing data collection. The RA2 will conduct the baseline measurements after obtaining the written consent and following comprehensive explanations about the study purpose and procedure and its ethical issues. After that, the participants will be assigned randomly to either study group or control group. Patients' outcomes at the ICCMWs will be measured at one week post-intervention using the same set of questionnaires as the baseline measures.

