Two groups of 3-4 participants in treatment group will be interviewed in a quiet interview room in the ICCMWs, or as preferred by the participants. Participants with significant positive changes, minimal changes and negative changes will be invited according to the baseline and Post-test 1 measurement. Interviews in a focus group format will be conducted to identify the strengths and limitations and therapeutic components from the participants' perspective. Interview questions will be developed based on an open and broad basis criterion (Appendix 2). Audio-recorded group sessions will also be used to examine the group process/dynamics and participants' involvement and appraisals of the group program.

The outcome measurements will be completed by the participants at three and six months after the interventions with the help of RA1 who will be blind to the participants' assigned groups. By self-reporting or case files reviewing, re-hospitalizations of the participants will also be examined and calculated and checked against their medical records. Participants' recruitment, interventions, data (outcomes) collection, and data analyses are outlined in a flow diagram of Appendix 3, as recommended by the latest CONSORT statement.

Data Analysis

Intention-to-treat (ITT) analyses (Fisher et al, 1989) will be used to provide a more conservative estimate of outcomes. By using IBM SPSS, version 23.0, all data on participants' socio-demographic illness-related characteristics, attendance and completion rate, and study outcomes will be numerically coded, summarized and analyzed. Repeated-measures ANOVA tests will be used to assess any significant differences on all dependent (outcome) variables within and between groups and across three post-tests (one week, 3 months and 6 months follow-up).

Sub-group analysis for participants who will complete all sessions and those completers, and the outliers which can have deleterious effects on statistical analyses will also be screened. Defined completers will be those who have attended at least eight sessions by which the main themes of the program are covered (Nose, Barbui and Tansella, 2003).

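### The SAP's statements on who scores PANSS, how and from what source conflict, so PANSS change scores may mix methods

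*SAP*

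**What the plan says.** Under Outcome Evaluation, the SAP describes PANSS as a scale scored by someone else and names its sources: "The PANSS ratings will be derived from clinical interview, clinical reports or family members over the past one week". The same section labels WHOQOL-100 as self-administered and AAQ-II and FFMQ as self-report, so the plan itself sets PANSS apart from them.

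The mode of assessment is described in several places:

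- Randomisation and recruitment procedure, before allocation: "Eligible participants will undertake a further interview on outcome measures prior to randomization". The same section refers to raters who gather the follow-up data and are kept blind.
- Data collection procedure, baseline: "The RA2 will conduct the baseline measurements after obtaining the written consent".
- Data collection procedure, 1 week: outcomes are "measured at one week post-intervention using the same set of questionnaires as the baseline measures".
- Data collection procedure, later visits: "The outcome measurements will be completed by the participants at three and six months after the interventions", helped by RA1. That sentence goes on to call RA1 blind to allocation.
- Data collection procedure, division of labour: "RA1 will be responsible for conducting the psychoeducation program and RA2 will be blinded and doing data collection".

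Psychotic symptoms are a secondary outcome at 1 week, 3 months and 6 months (Study Aim, Objectives and Hypotheses). Data Analysis applies repeated-measures ANOVA to every outcome and adds within-subject effect sizes. Adverse events reporting and monitoring uses a PANSS deterioration of 25% or more as a reporting trigger.

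**The concern.** A change in PANSS is interpretable only if the scale is scored in the same way at each visit. Two features of the plan leave that open.

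The first is the list of sources, which is joined by a plain *or*. It permits a score from an interview at one visit and from reports or a relative alone at another. The second is the sentence on the 3- and 6-month visits. Taken literally, it has a rater-scored scale filled in by the person being rated, with help from the person who delivers the control programme.

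At stake are the secondary analysis of psychotic symptoms and a safety report that uses the same scores. PANSS also matters because DASS-21 is self-reported by participants who know which programme they attended, whereas PANSS is the symptom scale that a blinded rater could score.

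**Working it through.** The SAP gives no figure on this point to reproduce. The check sets its statements side by side and then asks which results a method shift would reach.

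**What is fixed for PANSS at each visit**

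| Visit | Mode stated for the battery | Person named | PANSS excepted? |
|---|---|---|---|
| Baseline | Interview on outcome measures | RA2 | Not addressed |
| 1 week | Same questionnaires as baseline | None in that sentence; RA2 by the general division of labour | Not addressed |
| 3 months | Completed by participants | RA1 helps | No |
| 6 months | Completed by participants | RA1 helps | No |

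Three statements bear on PANSS at 3 and 6 months:

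1. It is rated from interview, reports or family (Outcome Evaluation).
2. Raters collect the follow-up data (Randomisation and recruitment procedure).
3. Participants complete the outcome measurements with RA1's help (Data collection procedure).

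Statements 1 and 2 are compatible. Statement 3 is not compatible with either unless PANSS is outside it, and the SAP does not say that it is. Nor does it say who rates PANSS at these two visits.

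**Which results would be affected**

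Assume for illustration that scoring by a given method adds an offset *m* to the score. For one arm:

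observed change = true change + (m at follow-up − m at baseline)

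Write D for the bracket. Then:

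- *Between arms:* observed difference in change = true difference + (D in the MBCTp arm − D in the PEp arm). If D is the same in both arms, the last term is zero and the group-by-time contrast is not biased.
- *Within arm:* the time effect and the numerator of the within-subject effect size are shifted by the full D, whether or not the arms share it.
- *25% report:* for a participant with baseline total B, a method shift of D adds 100 × D / B percentage points to the apparent deterioration (taken on the raw total). It can trigger a report, or mask one if D is negative, with no change in symptoms.

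**Can D differ by arm?** It can if the source, mode or assessor differs by arm. Two routes are open in the text. RA1 will have taught the control participants and so knows who they are. An informant may also know which programme the participant attends and disclose it, or be influenced by it. The SAP does not show that either will happen.

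**Size.** D cannot be estimated. The SAP gives no PANSS standard deviation, no inter-rater reliability and no difference between sources or modes.

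**The case against.** The strongest reply is that loose wording is being read too literally. Most of the battery is self-report, so a sentence saying that participants complete it is a natural shorthand. The word interview at baseline may mean no more than an assessment session. The only rule specific to PANSS is the list of sources, which is tied to no visit and so applies to all. The SAP also plans raters at follow-up. A statistical analysis plan may further leave rater instructions to the protocol or a manual.

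Much of this stands, and it limits what may be concluded. A reader might infer that PANSS change definitely mixes methods, with an interview at baseline and self-completion afterwards. The SAP does not establish that, because the reference to follow-up raters points the other way. A reader might also see a switch of mode between baseline and 1 week. The text argues against it: the 1-week sentence says the same set is used at both visits. Finally, a reader might infer that the comparison between arms is biased. A shift tied only to the visit would be shared by both arms and would leave that contrast largely alone.

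The conflict itself remains. This is not silence to be filled by a protocol. The document has its own data collection section, and that section disagrees with its own definition of the instrument. The reference to raters names no instrument, mode or source, so it adds a statement to reconcile and does not settle the matter. The permissive list of sources also remains under the most generous reading of the other sentences.

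**Conclusion.** The point holds as an internal conflict. The SAP does not fix the rater, mode and source of PANSS by visit. Read literally, it allows participant-completed scores at two of the three follow-up visits (3 and 6 months) and scores without an interview at any visit. Change scores *may* therefore mix methods; that they *will* is not shown.

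The main exposure is in time effects, within-subject effect sizes and the 25% deterioration report. Bias in the between-arm contrast requires source, mode or assessor to differ by arm. That is possible if RA1, or an informant who knows the programme, contributes to the score. The separation of these consequences assumes a method effect that simply adds to the score. Its magnitude cannot be derived from the document.

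PANSS is a secondary outcome, and the primary DASS-21 outcome is not affected by this point. The conflict should be resolved before follow-up begins, but it does not threaten the trial's main result.

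**What to change.** Reconcile the PANSS statements in Randomisation and recruitment procedure, Outcome Evaluation and Data collection procedure so that they say the following:

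- PANSS is scored by the blinded assessor, RA2 and not RA1, from a clinical interview at baseline, 1 week, 3 months and 6 months.
- Clinical reports and family information only supplement the interview and are used in the same way at each visit. Programme attendance is withheld from the rater.
- Completion by participants refers only to the self-report scales: DASS-21, ERQ, WHOQOL-100, AAQ-II and FFMQ-SF.

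The visits and a blinded data collector are already in the plan. The change is still more than wording, because the SAP names RA1 for the 3- and 6-month visits. RA2 would have to cover PANSS there, and the follow-up interviews would be longer. No analysis or sample size has to change.

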et al, 2005; Chadwick et al, 2009; Langer et al, 2012; Chien & Thompson, 2014). In Chadwick's most recent study (2016), which was the first RCT of group CBTp for voices, there was no significant effect on the primary outcome of psychological distress targeting people with distressing voices in a pragmatic randomized controlled trial. Though there was improvement in intensity of voice distress post-treatment, no effects on depression were found. The generalizability of the study is doubtful across other psychotic symptoms as distressing voices is only one of disturbing symptoms in the course of psychotic disorders.

[figure not shown]

Figure 1 The working mechanism of mindfulness to emotional distress in psychosis

The knowledge gap

Evidence on the effectiveness of mindfulness interventions for psychosis is inconclusive despite that the aforementioned studies have indicated that mindfulness approaches are associated with a decrease in distress, emotional dysregulation and social functioning. Most of the studies had very small number of participants, using non-randomized, non-controlled and inconsistent protocols and process regarding the mindfulness interventions. Particularly, the evidence of mindfulness interventions for regulating emotional dysregulation (such as anxiety, depression and hopelessness) in relation to positive and negative symptoms has not been addressed in the literature.

The knowledge gap is that there is no evidence on whether mindfulness-based intervention can have an effect on emotional distress and emotional regulation in patients with psychosis and subsequently alleviate the positive symptoms of these patients.

Study Aim, Objectives and Hypotheses

The aim of this controlled trial is to test the effectiveness of a mindfulness-based intervention for people with recent-onset psychosis in improving their emotional distress and in so doing this will have a positive effect on positive and negative symptoms, as well as psychosocial functioning.

It is hypothesized that in comparison to routine psychiatric care with Psychoeducation for Psychosis (PEp), the participants receiving Mindfulness-based Cognitive Therapy for Psychosis (MBCTp) will have significantly: -

- Primary outcomes: Decrease in emotional distress at 1-week, 3-month and 6-month follow-ups post-treatment.

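### The 3- and 6-month outcomes are assigned to RA1 as a blind helper, but RA1 leads the control-arm groups and cannot be blind; RA2 is the plan's blinded data collector

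*SAP*

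**What the plan says.** Four sections of the SAP bear on who collects outcomes.

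- **Interventions:** "The psychoeducation group will be conducted by a research assistant (RA1) who is an experienced psychiatric nurse". The programme is 12 weekly sessions.
- **Data collection procedure, opening:** "RA1 will be responsible for conducting the psychoeducation program and RA2 will be blinded and doing data collection". RA2 also takes the baseline measurements, before randomisation. The next assessment "will be measured at one week post-intervention using the same set of questionnaires as the baseline measures", with no assessor named in that sentence.
- **Data collection procedure, follow-up:** the outcome measures are completed "at three and six months after the interventions with the help of RA1 who will be blind" to the assigned groups.
- **Randomisation and recruitment procedure:** "Raters who collect follow-up data will also be blind to the identity of participants", and "storage of data will be kept separate from the therapists and raters who will be working in different rooms".
- **Study Aim, Objectives and Hypotheses:** the primary outcome is stated as "Decrease in emotional distress at 1-week, 3-month and 6-month follow-ups post-treatment".

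**The concern.** The person described as blind at 3 and 6 months is, by the plan's own definition, the control-arm group leader. Staff working from this document would find only one sentence that names a person for a post-treatment visit, and it names the wrong kind of person.

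The primary outcome, DASS-21, is self-reported, and participants know their own group at every visit. Assessor blinding does not remove that. What can be avoided is the asymmetry: one arm would report its distress in the presence of the person who taught it for 12 weeks, and the other arm would not. That difference coincides exactly with allocation, so neither the planned repeated-measures ANOVA nor any other analysis can separate it from a treatment effect.

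The exposure would be larger for PANSS, where "The PANSS ratings will be derived from clinical interview, clinical reports or family members over the past one week", but only if RA1 also rates it, which the document does not say. Re-hospitalization is checked against medical records and is less exposed.

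**Working it through.** **1. The sections side by side.** The plan gives no figure to reproduce here; the point rests on the text.

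| Section of the SAP | RA1 | RA2 | Rule |
|---|---|---|---|
| Interventions | leads the control groups | – | – |
| Data collection procedure, opening | leads the control groups | blinded, collects data | – |
| Data collection procedure, 3 and 6 months | helps with outcomes, said to be blind | – | – |
| Randomisation and recruitment procedure | – | – | follow-up raters blind; therapists and raters apart |

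RA1 knows the control participants from the sessions and can infer that the rest are in MBCTp. The first two rows therefore exclude the third. The last row names neither assistant, so it conflicts only through its general rule. No section describes a handover, a second RA1 or a different control-group leader.

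**2. Reach.** The primary hypothesis has three time points: 1 week, 3 months and 6 months. The contradictory sentence covers the last two. The 1-week visit is not affected by it.

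**3. What a helper effect could do (illustration only).** From the SAP: 41 per group, three post-tests, 5% significance level. Assumed, because the SAP gives no values: no true effect; a shift of s SD in one arm at 3 and 6 months only; equal variances and an equal within-person correlation r between visits, with r from 0.3 to 0.7.

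*Group main effect.* The average shift over three visits is 2s/3, and the SD of a participant's mean is √((1+2r)/3), so

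d_eff = (2s/3) / √((1+2r)/3), noncentrality = d_eff·√(41/2), t with 80 df.

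Example with s = 0.2, r = 0.5: d_eff = 0.1333/0.8165 = 0.163; noncentrality = 0.163 × 4.528 = 0.74; rejection rate 11.3%.

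*Group by time.* The squared deviations of (0, s, s) from their mean sum to 2s²/3, so

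λ = (41/2)(2s²/3)/(1−r), F with 2 and 160 df.

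Example with s = 0.2, r = 0.5: λ = 20.5 × 0.02667/0.5 = 1.09; rejection rate 13.9%.

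| Assumed shift s | Group effect, r = 0.3 / 0.5 / 0.7 | Group by time, r = 0.3 / 0.5 / 0.7 |
|---|---|---|
| 0.1 SD | 6.9 / 6.5 / 6.3% | 6.5 / 7.1 / 8.5% |
| 0.2 SD | 12.9 / 11.3 / 10.2% | 11.2 / 13.9 / 20.5% |
| 0.3 SD | 23.2 / 19.5 / 17.0% | 19.9 / 26.5 / 41.8% |

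These are two-sided rates. They include false findings in either direction.

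**The case against.** **It is probably a slip.** RA2's role as blinded data collector is not limited to any visit, the follow-up raters are to be blind, and the disputed sentence itself says the helper is blind. Only the digit in RA1 conflicts. This is a fair reading and probably the intended one, and under it the bias is zero. It does not settle the matter: the sentence is an instruction to staff, nothing else in the document overrides it, and followed literally it breaks the blinding that the plan claims.

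**The 1-week and PANSS gaps are minor.** RA2's general role can be read to cover both, and naming raters is often left to a protocol. That stands. Neither gap is a defect on its own; both are worth closing while the sentence is being corrected.

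**The error rates are not evidence.** The shifts and correlations are assumed, and the results depend on the model. If baseline enters as a fourth time level, which Data Analysis leaves open, the rates at 0.3 SD become 11.9–16.4% for the group effect and 24.1–52.2% for group by time. Direction also matters: if control participants under-report distress to their own leader, false main-effect claims in favour of MBCTp fall below the nominal 2.5%, to about 0.1–1.1% over the grid above. All of this is correct. The figures show only that a modest arm-dependent shift would be enough to distort the tests, and the finding does not depend on them.

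**Nobody assigned outcome collection to the MBCTp leader.** True. Excluding that person corrects no cited contradiction; it applies the therapist–rater separation evenly to both arms.

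**Conclusion.** The plan contradicts itself. RA1 as defined cannot be the blind helper at 3 and 6 months, and this affects two of the three primary time points. It must be corrected, because data collected under the literal reading could not be repaired in analysis. Confidence in the contradiction is high. Whether collection by the control-arm leader was ever intended is unknown, as are the size and direction of any bias; if RA1 is a slip for RA2, the bias is nil. No loss of planned power is claimed: the effect size of 0.63 and power of 0.80 in Sample size were set at post-intervention, which the disputed sentence does not cover.

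**What to change.** In Data collection procedure, replace RA1 with RA2 in the sentence on the 3- and 6-month measures. Name RA2 as assessor at 1 week, 3 months and 6 months, including for PANSS. Add that RA1 and the researcher who leads MBCTp take no part in outcome collection, so that this section agrees with Interventions and with Randomisation and recruitment procedure.

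The cost is one or two sentences and no extra staff. If RA1 was a slip, nothing else changes. If RA1 was intended, RA2 takes on somewhat more follow-up work.
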